### **Severe Cutaneous Adverse Events**

Severe cutaneous adverse reactions (SCARs) are a heterogeneous group of immunologically mediated drug eruptions. Although rare, these events are potentially fatal, and mainly constituted by erythema multiforme, acute generalized exanthematous pustulosis, Stevens-Johnson syndrome (SJS), Toxic Epidermal Necrolysis (TEN) and drug rash with eosinophilia and systemic symptoms (DRESS).

- For suspected SCARs, patients should be referred to a dermatologist for further diagnosis and management
- Atezolizumab should be withheld for patients with suspected SJS or TEN
- Atezolizumab should be permanently withdrawn for any grade confirmed SJS or TEN
- Caution should be used when considering the use of atezolizumab in a patient who has previously experienced a severe or life-threatening skin adverse reaction on prior treatment with other immune-stimulatory anticancer agents

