## **Appendix 11**

### **Risks Associated with Atezolizumab and Guidelines for Management of Adverse Events Associated with Atezolizumab**

Toxicities associated or possibly associated with atezolizumab treatment should be managed according to standard medical practice. Additional tests, such as autoimmune serology or biopsies, should be used to evaluate for a possible immunogenic etiology.

Although most immune-mediated adverse events observed with immunomodulatory agents have been mild and self-limiting, such events should be recognized early and treated promptly to avoid potential major complications. Discontinuation of atezolizumab may not have an immediate therapeutic effect, and in severe cases, immune-mediated toxicities may require acute management with topical corticosteroids, systemic corticosteroids, or other immunosuppressive agents.

The investigator should consider the benefit–risk balance a given patient may be experiencing prior to further administration of atezolizumab. In patients who have met the criteria for permanent discontinuation, resumption of atezolizumab may be considered if the patient is deriving benefit and has fully recovered from the immune-mediated event. *The decision to re-challenge patients with atezolizumab should be based on investigator's assessment of benefit–risk and documented by the investigator. The Medical Monitor is available to advise as needed.*

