## **DERMATOLOGIC EVENTS**

Treatment-emergent rash has been associated with atezolizumab. The majority of cases of rash were mild in severity and self limiting, with or without pruritus. Although uncommon, cases of severe cutaneous adverse reactions such as Stevens-Johnson syndrome and toxic epidermal necrolysis have been reported with atezolizumab. A dermatologist should evaluate persistent and/or severe rash or pruritus. A biopsy should be considered unless contraindicated. Management guidelines for dermatologic events are provided in [Table 9](#).

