**Table 9 Management Guidelines for Dermatologic Events (cont.)**

Event	Management
Dermatologic event, Grade 4	

Permanently discontinue atezolizumab and contact Medical Monitor.c

Stevens-Johnson syndrome or toxic epidermal necrolysis (any grade)	
Additional guidance for Stevens-Johnson syndrome or toxic epidermal necrolysis:
 

Withhold atezolizumab for suspected Stevens-Johnson syndrome or toxic epidermal necrolysis.

Confirm diagnosis by referring patient to a specialist (dermatologist, ophthalmologist or urologist as relevant) for evaluation and, if indicated, biopsy.

Follow the applicable treatment and management guidelines above.

If Stevens-Johnson syndrome or toxic epidermal necrolysis, permanently discontinue atezolizumab.

a Atezolizumab may be withheld for a longer period of time (i.e., >12 weeks after event onset) to allow for corticosteroids (if initiated) to be reduced to *the equivalent of*  $\leq 10$  mg/day oral prednisone. The acceptable length of the extended period of time must be *based on an assessment of benefit–risk by the investigator and in alignment with the protocol requirements for the duration of treatment and documented by the investigator*. The Medical Monitor is available to advise as needed.

b If corticosteroids have been initiated, they must be tapered over  $\geq 1$  month to *the equivalent of*  $\leq 10$  mg/day oral prednisone before atezolizumab can be resumed.

c Resumption of atezolizumab may be considered in patients who are deriving benefit and have fully recovered from the immune-mediated event. *The decision to re-challenge patients with atezolizumab should be based on investigator's assessment of benefit–risk and documented by the investigator (or an appropriate delegate)*. The Medical Monitor is available to advise as needed.

**Appendix 11: Risks Associated with Atezolizumab and Guidelines for Management of Adverse Events Associated with Atezolizumab (cont.)**

---

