**Table 10 Management Guidelines for Neurologic Disorders**

Event	Management
Immune-mediated neuropathy, Grade 1	

Continue atezolizumab.

Investigate etiology.

Immune-mediated neuropathy, Grade 2	

Withhold atezolizumab for up to 12 weeks after event onset.a

Investigate etiology and refer patient to neurologist.

Initiate treatment as per institutional guidelines.

If event resolves to Grade 1 or better, resume atezolizumab.b

If event does not resolve to Grade 1 or better while withholding atezolizumab, permanently discontinue atezolizumab and contact Medical Monitor.c

Immune-mediated neuropathy, Grade 3 or 4	

Permanently discontinue atezolizumab and contact Medical Monitor.c

Refer patient to neurologist.

Initiate treatment as per institutional guidelines.

Myasthenia gravis and Guillain-Barré syndrome (any grade)	

Permanently discontinue atezolizumab and contact Medical Monitor.c

Refer patient to neurologist.

Initiate treatment as per institutional guidelines.

Consider initiation of 1–2 mg/kg/day oral or IV prednisone or equivalent.

**Appendix 11: Risks Associated with Atezolizumab and Guidelines for Management of Adverse Events Associated with Atezolizumab (cont.)**

---

- a Atezolizumab may be withheld for a longer period of time (i.e., >12 weeks after event onset) to allow for corticosteroids (if initiated) to be reduced to *the equivalent of*  $\leq 10$  mg/day oral prednisone. The acceptable length of the extended period of time must be *based on an assessment of benefit–risk by the investigator and in alignment with the protocol requirements for the duration of treatment and documented by the investigator*. The Medical Monitor is available to advise as needed.
- b If corticosteroids have been initiated, they must be tapered over  $\geq 1$  month to *the equivalent of*  $\leq 10$  mg/day oral prednisone before atezolizumab can be resumed.

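### Appendix 11's general resumption sentence has no exception for confirmed SJS or TEN, so read literally it reopens a re-exposure that Section 5.1.2 and Table 9 close

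*Protocol*

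**What the plan says.** Three places in the protocol bear on dosing after confirmed Stevens-Johnson syndrome (SJS) or toxic epidermal necrolysis (TEN).

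- **Section 5.1.2, Severe Cutaneous Adverse Events:** "Atezolizumab should be permanently withdrawn for any grade confirmed SJS or TEN". The same subsection describes severe cutaneous reactions as a "heterogeneous group of immunologically mediated drug eruptions" that is rare but can be fatal. It sends suspected cases to a dermatologist.
- **Appendix 11, Table 9, any-grade SJS/TEN row:** "If Stevens-Johnson syndrome or toxic epidermal necrolysis, permanently discontinue atezolizumab". This instruction has no footnote marker. The Grade 4 dermatologic row directly above it carries footnote c, which allows resumption to be considered. The SJS/TEN row also says: "Follow the applicable treatment and management guidelines above".
- **Appendix 11, introduction:** "In patients who have met the criteria for permanent discontinuation, resumption of atezolizumab may be considered", provided the patient is deriving benefit and "has fully recovered from the immune-mediated event". The decision rests on the investigator's documented benefit-risk assessment, and the Medical Monitor is there to advise if asked.

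The Dermatologic Events text of Appendix 11 adds that, although uncommon, cases of "severe cutaneous adverse reactions such as Stevens-Johnson syndrome and toxic epidermal necrolysis have been reported with atezolizumab".

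**The concern.** Section 5.1.2 and Table 9 stop the drug for good after confirmed SJS or TEN. The Appendix 11 introduction says that meeting a permanent-discontinuation criterion need not be final, and it excludes no event. A site that follows the introduction literally could give atezolizumab again to a patient who has recovered from SJS or TEN. The withdrawal rule exists to prevent exactly that exposure.

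The check on such a decision is thin. Under the introduction it belongs to the investigator, and Medical Monitor involvement is optional. The SJS/TEN row, unlike the Grade 4 dermatologic row, does not tell the site to contact the Medical Monitor. The stake is patient safety; no estimate or analysis in the SAP depends on it.

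**Working it through.** This is a question of text, and the only arithmetic is a count of table rows.

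**1. Does the general sentence cover a confirmed SJS/TEN case?** It applies to patients who met the criteria for permanent discontinuation. Section 5.1.2 and Table 9 both make confirmed SJS or TEN, at any grade, such a criterion. The sentence also requires full recovery from an immune-mediated event, and Section 5.1.2 itself classes these eruptions as immunologically mediated. A recovered patient who is benefiting meets every condition. The sentence contains no exception.

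**2. Does the word *permanently* exclude resumption?** To see how Appendix 11 uses it, take every event row that instructs permanent discontinuation, including rows where that applies only if the event fails to resolve. Count those with a footnote allowing resumption.

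| Appendix 11 table | With resumption footnote / all such rows |
|---|---|
| 1 Pulmonary | 2/2 |
| 2 Hepatic | 4/4 |
| 3 Gastrointestinal | 3/3 |
| 4 Endocrine | 4/4 |
| 5 Ocular | 2/2 |
| 6 Myocarditis | 1/1 |
| 7 Infusion-related reactions and CRS | 3/3 |
| 8 Pancreatic | 3/3 |
| 9 Dermatologic | 2/3 (SJS/TEN without) |
| 10 Neurologic | 3/3 |
| 11 Meningoencephalitis | 1/1 |
| 12 Renal | 2/2 |
| 13 Myositis | 2/2 |
| 14 HLH/MAS | 0/1 |

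Rows with the footnote: 2+4+3+4+2+1+3+3+2+3+1+2+2+0 = 32. All rows: 2+4+3+4+2+1+3+3+3+3+1+2+2+1 = 34.

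So in this appendix permanent discontinuation normally leaves re-challenge open. Severity at any grade does not change that: the any-grade row for myasthenia gravis and Guillain-Barré syndrome in Table 10 also carries the footnote.

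**3. What does the missing footnote show?** SJS/TEN is one of only two rows without it, and the row immediately above has it. The natural inference is that re-challenge was not meant to be available. But the general sentence already applies to all permanent discontinuations, so the absence of a row footnote does not switch it off.

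**4. Is there an order of precedence?** None is stated. Section 5.1 names Section 5.1.2, Appendix 11 and Section 6 of the Investigator's Brochure together as the sources for discontinuation criteria. Section 5.1.2 sends sites to Appendix 11 and the Brochure for managing atezolizumab-related events.

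**5. Does the pointer in the SJS/TEN row add to the problem?** Slightly. It directs the reader to the rows above. There the Grade 3 row contains an instruction to resume after resolution, and the Grade 3 and Grade 4 rows carry footnote c. Those rows do not themselves govern SJS/TEN, so this is a secondary ambiguity.

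**The case against.** The strongest reply is that the specific rule governs the general one. Two explicit SJS/TEN instructions agree, and the introduction is only a preface. If the preface opened re-challenge everywhere, the row-by-row footnotes would be redundant. Reading them as marking where resumption applies gives every text a purpose. This is a reasonable reading and probably the sponsor's intent. The protocol never states it, though, and a site should not have to infer a prohibition from an absent superscript.

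Other points stand in part:

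- **The bar is itself inferred.** Nothing in the protocol expressly forbids re-challenge after SJS or TEN; the bar comes from the withdrawal wording and the missing footnote. That is true, and it is a further reason to write the bar down.
- **The count rests on text extracted from a PDF.** Footnote markers come through unevenly, and Table 13 shows no Grade 4 myositis row. If one row were missing, the count would be 32/35 or 33/35. The conflict does not depend on it, because the general sentence has no exception under any count.
- **Other safeguards exist.** Resumption is permitted and not directed. It requires benefit, full recovery and a documented assessment. Section 4.6.2 requires discontinuation for intolerable related toxicity or a condition that jeopardizes safety. That section does not bar later resumption.
- **The Investigator's Brochure may settle the matter.** It is not available here, so this cannot be checked.

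**Conclusion.** The concern holds. On a literal reading, the Appendix 11 introduction allows an investigator to consider re-exposure after confirmed SJS or TEN, against the evident intent of Section 5.1.2 and the any-grade row of Table 9. The conclusion rests on three things: the literal wording of the general sentence, the absence of any stated precedence in the protocol, and the inference that the withdrawal wording with no footnote was meant as a bar.

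The number of patients affected would be small. The documents give no SJS/TEN rate, so none is assumed. Because the reaction can be fatal, the text should be corrected. The sample size and the primary analysis do not change.

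**What to change.** In the resumption sentence of the Appendix 11 introduction, add: *except for confirmed SJS or TEN (any grade), for which atezolizumab must not be resumed*. This clause resolves the conflict.

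As a secondary change, add a line to the SJS/TEN row of Table 9 stating that the Grade 3 instruction to resume and footnote c do not apply to confirmed SJS or TEN. This removes the ambiguity of the pointer to the rows above.

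The sponsor should also confirm whether the same exception is intended for suspected HLH/MAS. The Table 14 row likewise has no resumption footnote, but the body of the protocol gives no separate dosing rule for it. This is a query only.

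The cost is one clause and one line, by protocol amendment or site letter, with no effect on sample size or analysis.

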## **Hemophagocytic Lymphohistiocytosis and Macrophage Activation Syndrome**

Immune-mediated reactions may involve any organ system and may lead to hemophagocytic lymphohistiocytosis (HLH) and macrophage activation syndrome (MAS), which are considered to be potential risks for atezolizumab.

*Clinical and laboratory features of severe CRS overlap with HLH, and HLH should be considered when CRS presentation is atypical or prolonged.*

Patients with suspected HLH should be diagnosed according to published criteria by McClain and Eckstein (2014). A patient should be classified as having HLH if five of the following eight criteria are met:

- Fever  $\geq 38.5^{\circ}\text{C}$
- Splenomegaly
- Peripheral blood cytopenia consisting of at least two of the following:
  - Hemoglobin  $< 90 \text{ g/L}$  ( $9 \text{ g/dL}$ ) ( $< 100 \text{ g/L}$  [ $10 \text{ g/dL}$ ] for infants  $< 4$  weeks old)
  - Platelet count  $< 100 \times 10^9/\text{L}$  ( $100,000/\mu\text{L}$ )
  - ANC  $< 1.0 \times 10^9/\text{L}$  ( $1000/\mu\text{L}$ )
- Fasting triglycerides  $> 2.992 \text{ mmol/L}$  ( $265 \text{ mg/dL}$ ) and/or fibrinogen  $< 1.5 \text{ g/L}$  ( $150 \text{ mg/dL}$ )
- Hemophagocytosis in bone marrow, spleen, lymph node, or liver
- Low or absent natural killer cell activity
- Ferritin  $> 500 \text{ mg/L}$  ( $500 \text{ ng/mL}$ )
- Soluble interleukin 2 (IL-2) receptor (soluble CD25) elevated  $\geq 2$  standard deviations above age-adjusted laboratory-specific norms

Patients with suspected MAS should be diagnosed according to published criteria for systemic juvenile idiopathic arthritis by Ravelli et al. (2016). A febrile patient should be classified as having MAS if the following criteria are met:

- Ferritin  $> 684 \text{ mg/L}$  ( $684 \text{ ng/mL}$ )
- At least two of the following:
  - Platelet count  $\leq 181 \times 10^9/\text{L}$  ( $181,000/\mu\text{L}$ )
  - AST  $\geq 48 \text{ U/L}$
  - Triglycerides  $> 1.761 \text{ mmol/L}$  ( $156 \text{ mg/dL}$ )
  - Fibrinogen  $\leq 3.6 \text{ g/L}$  ( $360 \text{ mg/dL}$ )

Patients with suspected HLH or MAS should be treated according to the guidelines in [Table 14](#) in appendix 11.

## **5.2 SAFETY PARAMETERS AND DEFINITIONS**

Safety assessments will consist of monitoring and recording adverse events, including SAEs and adverse events of special interest, performing protocol-specified safety laboratory assessments, measuring protocol-specified vital signs, and conducting other protocol-specified tests that are deemed critical to the safety evaluation of the study.

Certain types of events require immediate reporting to the Sponsor, as outlined in Section [5.4](#).

### **5.2.1 Adverse Events**

According to the ICH guideline for Good Clinical Practice, an adverse event is any untoward medical occurrence in a clinical investigation subject administered a pharmaceutical product, regardless of causal attribution. An adverse event can therefore be any of the following:

- Any unfavorable and unintended sign (including an abnormal laboratory finding), symptom, or disease temporally associated with the use of a medicinal product, whether or not considered related to the medicinal product
- Any new disease or exacerbation of an existing disease (a worsening in the character, frequency, or severity of a known condition), except as described in Section [5.3.5.10](#).
- Recurrence of an intermittent medical condition (e.g., headache) not present at baseline
- Any deterioration in a laboratory value or other clinical test (e.g., ECG, X-ray) that is associated with symptoms or leads to a change in study treatment or concomitant treatment or discontinuation from study drug
- Adverse events that are related to a protocol-mandated intervention, including those that occur prior to assignment of study treatment (e.g., screening invasive procedures such as biopsies)

### **5.2.2 Serious Adverse Events (Immediately Reportable to the Sponsor)**

A serious adverse event is any adverse event that meets any of the following criteria:

- Is fatal (i.e., the adverse event actually causes or leads to death)
- Is life threatening (i.e., the adverse event, in the view of the investigator, places the patient at immediate risk of death)

This does not include any adverse event that had it occurred in a more severe form or was allowed to continue might have caused death.

- Requires or prolongs inpatient hospitalization (see Section [5.3.5.11](#))
- Results in persistent or significant disability/incapacity (i.e., the adverse event results in substantial disruption of the patient's ability to conduct normal life functions)

- Is a congenital anomaly/birth defect in a neonate/infant born to a mother exposed to study drug
- Is a significant medical event in the investigator's judgment (e.g., may jeopardize the patient or may require medical/surgical intervention to prevent one of the outcomes listed above)

The terms "severe" and "serious" are not synonymous. Severity refers to the intensity of an adverse event (e.g., rated as mild, moderate, or severe, or according to National Cancer Institute Common Terminology Criteria for Adverse Events [NCI CTCAE]; see Section 5.3.3); the event itself may be of relatively minor medical significance (such as severe headache without any further findings).

Severity and seriousness need to be independently assessed for each adverse event recorded on the eCRF.

Serious adverse events are required to be reported by the investigator to the Sponsor immediately (i.e., no more than 24 hours after learning of the event; see Section 5.4.2 for reporting instructions).

### **5.2.3            Adverse Events of Special Interest (Immediately Reportable to the Sponsor)**

Adverse events of special interest are required to be reported by the investigator to the Sponsor immediately (i.e., no more than 24 hours after learning of the event; see Section 5.4.2 for reporting instructions). Adverse events of special interest for this study include the following:

- Pneumonitis
- Colitis
- Endocrinopathies: diabetes mellitus, pancreatitis, adrenal Insufficiency, hypothyroidism/hyperthyroidism and hypophysitis
- Hepatitis
- Transaminitis Grade  $\geq 2$  (AST or ALT  $>3x$  ULN and bilirubin  $>2x$  ULN ) OR AST/ALT  $>10x$  ULN
- Systemic lupus erythematosus
- Neurological: Guillain-Barre Syndrome, myasthenic syndrome or myasthenia gravis, meningoencephalitis
- Nephritis
- Ocular toxicities (e.g., uveitis, retinitis, optic neuritis)
- Myositis
- Myopathies, including rhabdomyolysis
- Vasculitis

- Events suggestive of hypersensitivity, infusion-related reactions, cytokine-release syndrome, HLH, and MAS
- Cases of potential drug-induced liver injury that include an elevated ALT or AST in combination with either an elevated bilirubin or clinical jaundice, as defined by Hy's law (see [Section 5.3.5.7](#))
- Suspected transmission of an infectious agent by the study drug, as defined below
  - Any organism, virus, or infectious particle (e.g., prion protein transmitting transmissible spongiform encephalopathy), pathogenic or non-pathogenic, is considered an infectious agent. A transmission of an infectious agent may be suspected from clinical symptoms or laboratory findings that indicate an infection in a patient exposed to a medicinal product. This term applies only when a contamination of the study drug is suspected.
- Cardiac toxicities of Grade  $\geq 2$  (e.g., atrial fibrillation, myocarditis, pericarditis)
- Autoimmune flare of Grade  $\geq 3$

### **5.3 METHODS AND TIMING FOR CAPTURING AND ASSESSING SAFETY PARAMETERS**

The investigator is responsible for ensuring that all adverse events (see [Section 5.2.1](#) for definition) are recorded on the Adverse Event Electronic Case Report Form (eCRF) and reported to the Sponsor in accordance with instructions provided in this section and in [Sections 5.4– 5.6](#).

For each adverse event recorded on the Adverse Event eCRF, the investigator will make an assessment of seriousness (see [Section 5.2.2](#) for seriousness criteria), severity (see [Section 5.3.3](#)), and causality (see [Section 5.3.4](#)).

#### **5.3.1 Adverse Event Reporting Period**

Investigators will seek information on adverse events at each patient contact. All adverse events, whether reported by the patient or noted by study personnel, will be recorded in the patient's medical record and on the Adverse Event eCRF.

**After informed consent** has been obtained **but prior to initiation of study drug**, only serious adverse events caused by a protocol-mandated intervention (e.g., invasive procedures such as biopsies, discontinuation of medications) should be reported (see [Section 5.4.2](#) for instructions for reporting serious adverse events).

**After initiation of study drug**, all adverse events will be reported until 30 days after the last dose of study drug and 90 days for serious adverse events or adverse events of special interest.

Instructions for reporting adverse events that occur after the adverse event reporting period are provided in [Section 5.6](#).

